10.7. Study Drug Handling and Disposal

Study drug will be sent to the study site under appropriate storage conditions. Upon receipt of study drug, study staff are to open the shipment, and verify that the amount and identity of the contents match that stated in the enclosed shipping form. The Sponsor (or designee) is to be notified immediately about any irregularities, discrepancies, or damage.

All study drug will be provided for use only in this study and is not to be used for any other purpose. The study staff will maintain a full record of study drug accountability as described in Section 10.6.

Upon completion of the study, used and unused study drug and study drug containers are to be returned to the Sponsor (or designee) or, if prior Sponsor approval is obtained, disposed of in accordance with applicable site procedures. Study staff must maintain documentation of any missing or unreturned study drug. The final disposition of all study drug received at the site is to be documented.

10.8. Product Quality Complaints

A product quality complaint (PQC) is defined as any suspicion of a product defect or deficiency related to manufacturing, labeling, or packaging (ie, any dissatisfaction relative to the identity, quality, durability, reliability, safety, effectiveness, or performance of a product, including its labeling or package integrity). A PQC may have an impact on the safety and efficacy of the product. Timely, accurate, and complete reporting and analysis of PQC information from studies are crucial for the protection of subjects.

All initial PQCs must be reported to the Sponsor or CRO by study-site personnel within 24 hours after being made aware of the potential defect. Whenever possible, the associated product should be maintained in accordance with the label instructions pending further guidance from the Sponsor.

11. SAFETY ASSESSMENTS

Safety evaluations, including AEs, concomitant medications, medical history, vital signs, body weight, physical examinations, standard 12-lead ECGs, and laboratory evaluations of safety will be performed as indicated in the Schedule of Assessments ([Appendix A](#) for the single dose segments and [Appendix B](#) for the multiple dose segments).

Although SAD-HS and all of the MAD segments will be conducted in a blinded manner (ie, subjects, Investigator, study-site personnel, and CRO staff not involved in PK sample analysis or regulatory reporting will be blinded to treatment), the Sponsor, including the Sponsor Medical Monitor, will be unblinded to treatment assignment to assess safety on an ongoing basis. The SD-CP and SD-UP segments are not placebo-controlled (ie, all subjects will receive EP547) and will be conducted in an unblinded manner.

11.1. Adverse Events

11.1.1. Definition of an Adverse Event

An AE is defined as any untoward medical occurrence in a subject administered a pharmaceutical product and which does not necessarily have a causal relationship with this treatment. An AE can therefore be any unfavorable or unintended sign (including a clinically significant abnormal laboratory finding), symptom, or disease temporally associated with the use of a medicinal (investigational) product.

Medical conditions present at baseline that worsen in severity or frequency after exposure to study drug are considered treatment-emergent AEs (TEAEs). Planned hospital admissions or surgical procedures for an illness or a disease that existed before administration of study drug, and for which the condition has not worsened since starting study drug, are not to be considered TEAEs/treatment-emergent SAEs. Events with emergency room visits that are less than 24 hours will also not be considered SAEs unless they meet one of the criteria listed in [Section 11.2.1](#).

Clinically significant abnormal laboratory tests, 12-lead ECG assessments, or vital sign results may, in the opinion of the Investigator, constitute an AE. However, whenever possible, the underlying diagnosis should be listed in lieu of associated abnormal results. Abnormalities deemed not clinically significant by the Investigator should not be reported as AEs.

11.1.2. Determining Severity of Adverse Events

The Investigator will assess the severity of an AE using the 3-point scale below:

- **Mild** - Awareness of a sign or symptom that is easily tolerated
- **Moderate** - Discomfort enough to cause interference with usual activity
- **Severe** - Incapacitating or causes inability to work or undertake usual activity

11.1.3. Determining Causality of Adverse Events

Causality refers to the relationship of the event to the study drug (EP547 or placebo). The Investigator will assess the causality of the event according to the following criteria:

- **Not related** - A reaction for which sufficient data exist to indicate that the etiology is unrelated to the study drug.
- **Related** - A reaction that follows a reasonable temporal sequence from administration of study drug; that follows a known or expected response pattern to the study drug, which may or may not reasonably have been produced by a number of other factors including underlying disease, complications, concomitant drugs, or concurrent treatments; and/or that could not be reasonably explained by other factors such as underlying disease, complications, concomitant drugs, or concurrent treatments; and/or disappears or decreases on cessation or reduction in study drug dose; and/or reappears or worsens when the study drug is administered.

11.1.4. Recording Adverse Events

All AEs must be recorded in the source documents and in the eCRFs provided by the Sponsor from the signing of the ICF until the end of study participation. AEs will be assessed for likelihood of causal relationship to the study drug (EP547 or placebo) and severity.

The new onset of signs, symptoms, or other findings that occur before signing of the ICF will be captured as medical history (Section 11.4).

11.1.4.1. Special Instructions for Recording Adverse Events in the eCRF

Diagnosis versus Signs and Symptoms

If a diagnosis is known at the time of reporting, this should be recorded in the eCRF rather than the individual signs and symptoms (eg, record only hepatitis rather than elevated transaminases, bilirubin, and jaundice). However, if a constellation of signs and/or symptoms cannot be medically characterized as a single diagnosis or syndrome at the time of reporting, each individual event should be recorded as an SAE or AE on the eCRF. If a diagnosis is subsequently established, it should be reported as follow-up and should replace the individual signs and/or symptoms as the event term on the eCRF, unless the signs/symptoms are clinically significant.

Adverse Events Occurring Secondary to Other Events

In general, AEs occurring secondary to other events (eg, clinical sequelae or a cascade of events) should be identified by their primary cause. For example, if severe vomiting is known to result in dehydration, it is sufficient to record only vomiting as an SAE or AE on the eCRF. However, medically significant AEs occurring secondary to an initiating event that are separated in time should be recorded as independent events on the eCRF. For example, if severe vomiting leads to acute renal failure, both events should be recorded on the eCRF.

Persistent or Recurrent Adverse Events

A persistent AE is one that extends continuously, without resolution, between subject evaluation timepoints. Such events should only be recorded once on the eCRF. If a persistent AE becomes more severe or lessens in severity, it should be recorded as a new AE on the eCRF.

A recurrent AE is one that occurs and resolves between subject evaluation timepoints, and subsequently recurs. Each reoccurrence of an AE should be recorded on the eCRF.

Abnormal Laboratory Values or Vital Signs

Protocol defined laboratory values and vital signs will be reported as AEs if the abnormal laboratory or vital sign result:

- Requires an adjustment in the study drug(s) or discontinuation of treatment;
- Requires additional testing, excluding repeat testing of the lab in question, or surgical intervention;
- Is associated with accompanying signs/symptoms that are not considered part of a pre-existing diagnosis or syndrome; or
- Is considered clinically significant by the Investigator

If an abnormal laboratory value or vital sign is the result of an evaluation of clinical signs, symptoms, or suspected diagnosis during the conduct of the study, the signs/symptoms or diagnosis should be reported as an AE (or if appropriate, an SAE) only if clinically significant, and the associated laboratory value or vital sign should be considered additional information that must be collected on the relevant eCRF.

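### Section 11.1.4.1 can leave a symptom or diagnosis unrecorded as an AE when its work-up finds an abnormal result, in conflict with Sections 11.1.1, 11.1.2 and 11.1.4 and its own bullet list

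*Protocol*

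**What the plan says.** Four parts of Protocol Section 11.1 bear on whether a symptom is recorded as an AE.

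- **Definition (11.1.1).** "An AE is defined as any untoward medical occurrence in a subject administered a pharmaceutical product". The section continues: "An AE can therefore be any unfavorable or unintended sign (including a clinically significant abnormal laboratory finding), symptom, or disease temporally associated". The significance qualifier sits inside the parenthesis on laboratory findings. The section's closing paragraph applies the same test to laboratory, ECG and vital sign results.
- **Severity (11.1.2).** The lowest AE grade, Mild, is "Awareness of a sign or symptom that is easily tolerated".
- **Recording (11.1.4).** "All AEs must be recorded in the source documents and in the eCRFs provided by the Sponsor".
- **Special instructions (11.1.4.1).** A known diagnosis replaces its individual symptoms; symptoms that cannot be unified are each recorded. Four alternative bullets then say when a laboratory value or vital sign is itself an AE. The third is that it "Is associated with accompanying signs/symptoms that are not considered part of a pre-existing diagnosis or syndrome"; clinical significance is a separate, fourth bullet. The last paragraph covers an abnormal value found while evaluating a symptom or suspected diagnosis. There, "the signs/symptoms or diagnosis should be reported as an AE (or if appropriate, an SAE) only if clinically significant". The abnormal result is kept on the eCRF only as supporting information.

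AEs are the first primary safety outcome (Protocol 15.2.1). Section 15.4 assesses safety by comparing AE frequency and severity. Section 7.3.1 uses the number and severity of AEs, with their nature and relationship to drug, to judge whether a dose level is well tolerated.

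**The concern.** In the last paragraph of 11.1.4.1 the significance test moves from the test result to the symptom or diagnosis. Read literally, finding an abnormal value raises the bar for recording the symptom that prompted the test. The same complaint with no test, or with a normal one, has no such bar to clear. No threshold is given for when a symptom counts as clinically significant.

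The paragraph also conflicts with the third bullet just before it. The bullet makes the abnormal result an AE when new symptoms accompany it; the paragraph reduces the result to supporting information.

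At stake is the completeness and consistency of the AE count. The study is multi-center, so sites may resolve the conflict differently. AE incidence would then depend partly on whether a test was done and which sentence was followed.

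**Working it through.** The plan states no figure to reproduce, so the check is a comparison of the rules, followed by a scale calculation.

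**Step 1: one event under each rule.** Take a new, easily tolerated symptom that the Investigator judges not clinically significant.

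| Situation | Rule followed | Result |
|---|---|---|
| No test done, or test normal | 11.1.1, 11.1.2, 11.1.4 | Mild AE under the symptom term |
| Evaluation yields an abnormal value | 11.1.1, 11.1.2, 11.1.4 | Mild AE under the symptom term |
| Evaluation yields an abnormal value | 11.1.4.1, third bullet | AE under the laboratory or vital sign term |
| Evaluation yields an abnormal value | 11.1.4.1, last paragraph | No AE; value kept as supporting information |

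Once an abnormal value is found, three outcomes are possible for the same event.

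**Step 2: does the SAP recover the event?** SAP 13.1 restricts AE summaries to TEAEs, so an event never recorded as an AE cannot appear. The value stays on the eCRF, but a value taken to evaluate a symptom may well be unscheduled. SAP 3.1, 13.2 and 13.3 limit summary tables to scheduled results and leave unscheduled ones to the listings. The event can therefore be absent from the AE tables while its value is absent from the laboratory or vital sign tables.

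**Step 3: scale.** Protocol 7.1.2 and 7.1.3 give 8 to 12 subjects per MAD-CP or MAD-UP dose level, allocated 3:1.

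- EP547 per level: 8 × 3/4 = 6 to 12 × 3/4 = 9.
- Placebo per level: 8 × 1/4 = 2 to 12 × 1/4 = 3.
- SAP 3.7.1 pools placebo in these segments only if there is more than one dose level. Over two levels: 2 + 2 = 4 to 3 + 3 = 6.

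One subject whose only event goes unrecorded changes incidence by 1/n:

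| Group | n | Change (percentage points) |
|---|---|---|
| EP547, one dose level | 9 to 6 | 1/9 = 11 to 1/6 = 17 |
| Placebo, one dose level | 3 to 2 | 1/3 = 33 to 1/2 = 50 |
| Placebo pooled over two levels | 6 to 4 | 1/6 = 17 to 1/4 = 25 |

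These figures show what one lost event would do. They say nothing about how many are lost.

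**The case against.** The strongest defence is that 11.1.4.1 exists to narrow the general rule. It already tells sites to record a diagnosis in place of its symptoms and usually to omit secondary events, so the last paragraph may be a loosely worded instruction to use one term per event. This does not remove the conflict. A one-term rule needs one term to survive, whereas here the condition governs both the symptoms and the diagnosis, and the value is set aside as well.

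Several limits do stand:

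- The protocol requires all AEs to be recorded, not every symptom.
- Not clinically significant is an Investigator's judgement and is not the same as Mild, which is defined by tolerability.
- The third bullet offers another route into the AE data, so loss is possible rather than certain.
- The trigger is narrow. Abnormal values found at routine scheduled checks do not activate the paragraph.
- The abnormal value must still be collected, laboratory and vital sign data are primary outcomes in their own right, and the Safety Review Team reviews them individually (Protocol 7.1).

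A reader might infer that the comparison with placebo is biased. Investigators are blinded in every placebo-controlled segment (Protocol 9.3.2), and nothing in the documents suggests the condition would operate differently by arm. A reader might also infer that SAEs could be lost, since the sentence mentions them. Section 11.2.2 separately requires a report for each SAE, and an event meeting the criteria in 11.2.1 would hardly be judged not clinically significant.

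**Conclusion.** The conflict is real and the sentence is wrong as written. Some symptomatic events judged not clinically significant may be missing from the primary AE outcome, or may appear under different terms at different sites, and the SAP does not restore them.

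It would go too far to say that mild events with objective findings do drop out, or that incidence is understated by a known amount. Loss depends on an Investigator's judgement and on which sentence is followed, and the documents give no basis for a frequency. The shifts for one subject assume that the unrecorded event was that subject's only one. The 33 to 50 point placebo figure also assumes a single dose level in that patient segment.

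The rules for stopping escalation or holding dosing (Protocol 7.3.3 and 7.3.4) turn mainly on severe or serious related events and are unlikely to be affected. The exposure is in the AE tables and the tolerability judgement of 7.3.1. The correction should be made, but this does not undermine the study.

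**What to change.** Three linked changes to Protocol 11.1.4.1:

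1. In the last paragraph, delete the closing clinical-significance condition. The symptoms or diagnosis are then recorded as an AE (or SAE) under 11.1.1, 11.1.4 and the diagnosis rule, with the abnormal value as supporting information.
2. In the third bullet, state that when the accompanying symptom or diagnosis is itself recorded as the AE, the value is not recorded as a second AE. Without this, the first change leaves the conflict with the bullet in place and invites double recording.
3. Keep the clinical-significance test for isolated laboratory and vital sign results.

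The cost is a short amendment, which needs ethics approval (Protocol 16.9), matching site instructions, and a few more AEs recorded. The food-effect addendum (Section 5) reports that conduct of SAD-HS and MAD-HS was complete and patient evaluations were ongoing. Those healthy-subject segments, and any patient data collected before the amendment, would have been recorded under the existing wording. The CSR should say so, so that AE incidence is not compared across segments as if the recording rule had been the same.

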11.2. Serious Adverse Events

11.2.1. Definition of a Serious Adverse Event

An SAE is any untoward medical occurrence, that at any dose:

- Results in death;
- Is life-threatening, ie, the subject is, in the opinion of the Investigator, at immediate risk of death from the event as it occurred, (it does not include an event that, had it occurred in a more severe form, might have caused death);
- Requires hospital admission or prolongs hospitalization. Planned hospital admissions or surgical procedures for an illness or a disease that existed before administration of study drug, and for which the condition has not worsened since starting study drug, are not to be considered SAEs. Emergency room visits that are less than 24 hours will also not be considered SAEs;
- Results in persistent or significant disability or incapacity;
- Is a congenital anomaly/birth defect; or
- Is a medically significant event that, based on appropriate medical judgment, may jeopardize the subject and may require medical or surgical intervention to prevent one of the outcomes listed above.

Note: A distinction should be drawn between SAEs and severe AEs. Severity is a measure of the intensity of an AE, while the criteria for seriousness are indications of adverse subject outcomes for regulatory reporting purposes. A severe AE is not necessarily considered an SAE. For example, a headache that persists for several hours may be considered a severe AE but not an

SAE. Conversely, a wound infection that may be considered minor could be an SAE if it prolonged hospitalization.

11.2.2. Reporting Serious Adverse Events

The Investigator and the Sponsor will monitor safety for this study. A Serious Adverse Event Report (SAER) Form is to be completed for each SAE occurring after signing of the ICF until 30 days after the last dose of study drug, regardless of causality. The SAER Form must be submitted to the Sponsor or designee within 24 hours of the Investigator's first awareness of the event. Follow-up information to all SAEs should be submitted to the Sponsor, or designee, in the same timeframe as initial reports.

All SAE reports must be **reported within 24 hours of the Investigator's knowledge of the event** to [REDACTED]. Any supporting documentation (eg, medical records) sent to Novotech with the SAER Form must have subject identifying information (eg, subject names, subject addresses, and medical records number) redacted by the site.

All SAEs will be followed until resolution or medical stabilization (in cases where resolution would not be expected).

In accordance with applicable regulations and local laws, the Sponsor or designee will report all serious and unexpected AEs assessed as related to study drug by the Investigator and/or Sponsor, to the regulatory authorities within the required timeframe. The Investigator will be responsible for reporting this safety information to their IRBs/IECs.

If the Investigator becomes aware of an SAE any time after study completion and determines it is related to the study drug, the SAE must be reported to the Sponsor within 24 hours of the Investigator's knowledge of the SAE.

11.2.3. Pregnancy

Pregnancy in and of itself is not an AE, although pregnancies occurring in subjects or partners of male subjects are considered immediately reportable events. If a pregnancy occurs in a subject, study drug must be discontinued immediately. The pregnancy must be reported to Novotech via email at [REDACTED] within 24 hours of the Investigator's knowledge of the pregnancy using the Pregnancy Reporting Form.

The Investigator will follow the pregnant woman until completion of the pregnancy, and must notify the Sponsor, or designee, of the outcome within 24 hours of the Investigator's knowledge of the pregnancy outcome. The Investigator will provide this information on the Pregnancy Reporting Form. This notification includes pregnancies resulting in live, "normal" births.

If the pregnant subject experiences an SAE during pregnancy, or the outcome of the pregnancy meets the criteria for immediate classification as an SAE (ie, spontaneous abortion [any congenital anomaly detected in an aborted fetus is to be documented], stillbirth, neonatal death, or congenital anomaly), the Investigator should follow the procedures for reporting SAEs (ie, report the event to Novotech via email at [REDACTED] within 24 hours of the Investigator's knowledge of the event).

All neonatal deaths and congenital anomalies that occur within 30 days of birth (regardless of causality) should be reported as SAEs to the Sponsor. In addition, any infant death or congenital

anomaly occurring after study completion that the Investigator suspects is related to the *in utero* exposure to the study drug should also be reported to the Sponsor.

11.3. Concomitant Medications

The addition of concomitant medications is not permitted during the study, except for acetaminophen (up to 1 gram per 24-hour period) as permitted by the Investigator for the treatment of headache or any other pain. Other medication to treat AEs may only be prescribed if deemed necessary by the Investigator. For subjects with cholestatic or uremic pruritus, dosages of any concomitant therapies are to remain stable for the duration of this study unless adjustments are needed for subject safety.

Any change in regimen for any concomitant medication other than acetaminophen must be reported to the Sponsor in a timely manner and done in consultation with the Medical Monitor if subject safety is not immediately compromised.

All medications taken within 14 days before Screening and details of concomitant medications from Screening through the end of study participation should be recorded in the subject's source documents and in the eCRF. In addition, medications taken to treat a cholestatic disorder or ESRD within 12 weeks before Screening or medications known to impact pruritus within 4 weeks before Screening should also be recorded.

11.4. Medical History

The Investigator will collect and review the subject's medical history to evaluate the subject's eligibility for study participation. The new onset of signs, symptoms, or other findings that occur from before signing of the ICF will be captured as medical history.

11.5. Vital Signs

Vital signs, including supine systolic and diastolic blood pressure, pulse rate, oxygen saturation, body temperature, and respiratory rate, will be measured after at least 5 minutes of rest.

For the single dose segments, vital signs will be measured at Screening; predose and at 1, 2, 4, 9, and 12 hours postdose on Day 1; 24 hours postdose on Day 2; 48 hours postdose on Day 3; on Day 8; and Early Study Termination, if applicable. The time margin for vital signs is 15 minutes for 1 and 2 hours postdose and 15 minutes for 4, 9, and 12 hours postdose.

For the multiple dose segments, vital signs will be measured at Screening; predose and at 1, 2, 4, 9, and 12 hours postdose on Day 1; predose on Days 2 to 7; 24 hours after the last dose on Day 8; on Days 14 and 21; and at Early Study Termination, if applicable. The time margin for vital signs is 15 minutes for 1 and 2 hours postdose and 20 minutes for 4, 9, and 12 hours postdose.

